9.9.1.1 Project management

The clinical project manager is responsible for the following (selection of items):

- Development of the clinical investigation plan and possible amendments.
- Coordination of all study-related activities dedicated to the sponsor.
- Support of investigational sites during the study (obtaining ethic committee votes, etc.).
- Continuous information of investigational sites and clinical monitors on study progress.
- The clinical project manager is supported by other staff members of the sponsor (e.g. in-house clinical project associates, data assistants, data managers).

9.9.1.2 Data Management

The data manager is responsible for the following items (selection of items):

- Development and maintenance of the clinical data management system (CDMS; iMedNet of the company MedNet Solutions Inc, Minnetonka, MN 55305 USA).
- Development of the data management plan.
- Development of the eCRF user guide.
- Data management.

9.9.1.3 Biostatistician

The statistician is responsible for the following items (selection of items):

- All statistical aspects within the clinical investigation plan.
- Statistical analysis for clinical investigation report.

The statistician will be supported by other staff members of the sponsor.

[figure not shown]
9.9.1.4 Monitor

The sponsor names clinical monitors for each participating investigational site prior to initiation of the respective site. Names and contact data will be provided to the investigational sites in due time. In case of changes, the investigational site will be informed by the sponsor. An adequate monitoring will be ensured by the sponsor. Monitoring will be conducted according to the SOPs of the sponsor. Responsibilities of the clinical monitors are described in section 10 of this document.

9.9.2 Responsibilities of the investigators

9.9.2.1 Coordinating Investigator (CI)

The clinical study BIO|MASTER.Cor Family is coordinated by:

The responsibilities of the CI are listed in the following:

- Development and review of the clinical investigation plan.
- Procurement of the central vote of an ethics committee.
- Performance and progress control of the study.
- Continuous assessment of the risk/benefit ratio.

- If necessary, decision on premature study termination in consultation with the sponsor.
- Contribution to coordination of publication and presentations of study results.
- Advising all investigators in medical questions related to the study or study conduction.
- Evaluation of potential unexpected adverse events.
- Discussion of possible interim results.
- Cooperation in writing of the final clinical report.

The Coordinating Investigator is supported by the clinical Project Manager and other members of the sponsor.

In addition, the CI has the same rights and duties as other principal investigators.

9.9.2.2 Investigator

The study shall be conducted by qualified investigators.

Rights and duties of the investigators are specified in the clinical investigation plan and are further regulated in the contract for study conduct. The principal investigator named in the study contract may share the rights and duties with investigators and other staff at the investigational sites. Nevertheless, the principal investigator retains the main responsibility for proper study conduct with respect to the following duties:

- Registration of the study to the bodies responsible for the investigational site (e.g. hospital administrative department).
- Notification to competent authority (if applicable) responsible for the investigational site.
- If required, obtaining of a positive vote of the ethics committee responsible for the investigational site.
- Adverse Event reporting according to the clinical investigation plan.
- Recruitment of suitable patients in an adequate time frame.
- Patient information and obtaining of written informed consent of the patient according to the requirements of the CIP.
- Safe and efficient use of devices.
- Inform the sponsor about new study team members before authorizing them for study related activities.
- Provide the sponsor with required documentation for assessing the qualification of study team members.
- Authorize co-investigators only after documented adequate study specific training.
- Discourage patients to consent for other interventional clinical investigations, in case the investigator is aware of such intentions beforehand. Inform the sponsor and follow the sponsor's guidance, in case a patient has already been enrolled into another interventional clinical investigation. Obtain the sponsors permission before enrolling the patient into another interventional clinical investigation.
- Conduct of the study according to the CIP.
- Data collection and data entry in accordance with the requirements of the CIP.
- Providing supporting material, if necessary.
- Submission of safety reports and protocol deviations to ethics committee and competent authorities (if applicable).
- Support of monitoring and auditing activities.
- Confidential treatment of all study-related documents and information.

In case the principal investigator (or authorized staff) does not fulfill the requirements defined, the sponsor is entitled to exclude the respective investigational site or principal investigator from further study participation.

9.10 Possible influencing factors on outcome or interpretation of results

No factors that could influence the outcome or interpretation of the results are known at this time.

10 MONITORING PLAN

The responsibility of BIOTRONIK as sponsor is to ensure protocol and regulatory compliance through proper monitoring of the study. BIOTRONIK is required to ensure that the devices under investigation are used under the immediate direction of an investigator. As the investigator, the physician is responsible for conducting the study in accordance with the signed clinical trial agreement, the clinical investigation plan, applicable laws and/or local regulations and any conditions of approval imposed by the reviewing EC.

The entries in the eCRF will be reviewed and source data verified at the investigational site by monitors (authorized BIOTRONIK personnel, Clinical Research Associates-CRAs, or by authorized BIOTRONIK designees) to ensure that the investigator and the clinical investigation team conducts the clinical investigation in accordance with the CIP, The Declaration of Helsinki, ISO 14155, and applicable laws and regulations to ensure adequate protection of the rights, safety and wellbeing of subjects and the quality and integrity of the resulting data.

A monitor will visit the study site periodically during the study. All actively enrolling sites will have at least an initiation visit, one early monitoring visit after the first patients have been enrolled in order to detect and prevent systematic errors in study conduct or documentation, and a close-out visit. Additional monitoring visits will be conducted based on risk related criteria such as e.g. recruitment rate and documentation quality. Details on criteria for initiating monitoring visits as well as strategy and extent of source data verification are subject to a detailed monitoring plan developed by BIOTRONIK as an internal document.

Monitoring visits will assure, amongst others, that the facilities are still acceptable, that the CIP is being followed, that the EC/CA has been informed about approved CIP changes as required, that records on study conduct and data collection are complete and present, that appropriate and timely reports have been made to the sponsor and the authorities, and that the investigator is carrying out all agreed activities.

Assessments of the study site will include but will not be limited to the following:

1. Completion and submission of the required electronic case report forms (eCRFs) and other applicable study documentation
2. Continued acceptability of the facilities
3. Adherence to the clinical investigation plan
4. Adherence to current version of ISO 14155 and applicable local regulations and laws

If a monitor becomes aware that an investigator is not complying with the requirements mentioned above, the monitor is obliged to notify BIOTRONIK study management. BIOTRONIK will evaluate the non-compliance and issue corrective actions, discontinue enrollment or as a last measure close the clinical investigational site (see section 14 and 20).

11 STATISTICAL CONSIDERATIONS

11.1 Statistical design, method and analytical procedures

To test the primary hypothesis an exact binomial tests is carried out. Additionally, an exact 2-sided 95% confidence interval will be generated.

For continuous variables descriptive statistics (mean, standard deviation, median, minimum, maximum and quartiles) will be calculated. For nominal variables absolute and relative frequencies will be calculated based on non-missing data. Ordinal variables are described similarly as continuous data (minimum, 1. quartile, median, 3. quartile, and maximum) or by absolute and relative frequencies based on non-missing data of each category.

All calculations will be carried out using validated software, e.g. SAS 9.4 © or upgrade.

Further details will be provided in the separate Statistical Analysis Plan (SAP).

11.2 Sample size

The sample size for the primary hypothesis is based on an exact test for binomial proportions. Thereby a SADE-free rate in the population of 98% was assumed, which yields together with the null proportion from the primary hypothesis to a sample size N=114.

Considering potential non-replaceable drop-outs after implantation, $N_{\text{incl do}} = 127$ patients have to be enrolled.

11.3 Level of significance and the power of the study

Because of the importance of accepting a true primary alternative hypothesis in this clinical investigation of a new device family that will serve as a basis for future developments, a minimum statistical power of 95% was used for sample size calculation based on the primary hypothesis. Thereby the power saw-tooth function for binomial endpoints is always above this limit for the given or any higher sample size.

For the statistical test of the two-sided primary hypothesis, a two-sided p value less than 5% will be considered statistically significant.

11.4 Expected drop-out rate

It is expected that approximately 10% of the enrolled patients cannot be included in the analysis set for the primary hypothesis, e.g. due to lost-to follow-up or withdrawal of patient consent of patients without primary endpoint before the pre-specified time window, respectively. This was already considered in the sample size calculation.

11.5 Pass/fail criteria

The clinical investigation is deemed to be passed, if the primary Alternative Hypothesis can be accepted based on the given level of significance.

11.6 Provision for an interim analysis

An interim analysis is planned after the completion of the 3-month follow-ups of all enrolled patients without prior study termination and final documentation of all prior primary endpoints. After this point in time, the data for testing the primary hypothesis will not be changed until the final analysis, and thus no multiplicity adjustment is required. Analysis of all other data and endpoints is explorative, therefore no multiplicity adjustment is required, either.

On request specific data might be provided to the competent authorities. Such kind of preliminary analysis would not bias the further data because no investigator except the Coordinating Investigator will be informed about the results. Except for safety reasons, no

instruction for the further conductance of the clinical investigations will be made based on such preliminary analysis.

11.7 Termination criteria

As this study is part of the overall post-market clinical follow-up plan, no termination criteria are pre-defined for the study based on statistical considerations.

Criteria and procedures for suspension or premature study termination are defined in section 20.1.

11.8 Procedures for reporting of deviations to the statistical plan

A separate Statistical Analysis Plan will be finalized at least 3-months after CDMS-go-live and can be updated before CDMS-freeze or closure. Any deviation from the valid version of the Statistical Analysis Plan will be indicated in the Statistical Analysis Report and Clinical Investigation Report.

11.9 Specification of subgroups

For this clinical investigation there is no specification of subgroups in the sense that analyses will be repeated for subsets of the pre-specified analysis set. However, there are different analysis sets defined for the primary and secondary endpoints.

11.10 Procedure for accounting of all data for analysis

All data are entered in a CDMS by the investigators via an electronic data capture system (iMedNet, MedNet Solutions). The Home Monitoring data are stored in the BIOTRONIK Home Monitoring Service Center (HMSC). For the analysis of such data, exports from the Clinical Data Warehouse will be used, a validated pseudonymized mirror of the HMSC. Exports from these databases will be analyzed with common validated statistical software packages (e.g. SAS 9.4 or updates, SAS Institute GmbH).

11.11 Handling of missing, unused and spurious data

Missing or spurious data will not be imputed.

11.12 Exclusion of data from confirmatory data analysis

In the following cases, data are to be excluded from analysis or prevented from inclusion into analysis:

- Exclusion of patients from the analysis set of the primary hypothesis:
 - No data is allowed to be collected and included in the absence of a documented informed consent
 - Patients that are erroneously enrolled despite violation of inclusion or exclusion criteria at the time of enrollment
 - Patients without primary endpoint but premature study termination as defined for the primary endpoint are not included in the analysis set to avoid an over-estimation of the SADE-free rate.
- Exclusion of data from patients included in the analysis set of the primary hypothesis:
 - Any event occurred later than the pre-specified time window after implantation as defined for the primary endpoint.
 - SADEs will be adjudicated by an internal adjudication board, whereby the seriousness and device relatedness will be re-examined. If any amply documented external physical influence (e.g. accident, sport, twiddling) or other causative AE led to the SADE, the SADE does not contribute to the endpoint.

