5.3 Justification

The above mentioned studies indicate the safety and efficacy of the predecessor devices of the Cor Family ICDs and the Plexa S DX lead, as well as the safety and efficacy of the DX system.

The devices of the Cor Family and the Plexa S DX lead have obtained the CE mark based on technical documentation and a clinical evaluation, according to European regulations (Directive 90/385/EEC on Active Medical Devices (AIMDD)). In addition, according to MEDDEV¹, the manufacturer is obliged to perform a Post Market Clinical Follow-up (PMCF) study in order to identify and evaluate residual unknown risks associated with the use of the devices that remained unrevealed even after risk analysis, risk mitigation and successful conformity assessment. This request is based on the corresponding European guidelines whereby a PMCF study should be considered where CE marking was based on equivalence². This includes the application of new technology in medical devices.

The BIO|MASTER.Cor Family Study design is very similar to that of the BIO|MASTER.Ilivia Family/Plexa study and the BIO|MASTER.Edora study regarding endpoints and general design, given that the devices share a number of features.

In order to provide further supporting clinical evidence with regard to Acticor/Rivacor ICD's/CRT-D's safety and efficacy, and the identification of possible residual risks, one primary endpoint and three secondary endpoints were defined.

The primary endpoint assesses the safety of the Cor Family. For the safety endpoint the SADE-free rate is calculated based on all SADEs related to the Acticor/Rivacor ICDs/CRT-Ds occurring until 3 months post implantation. The threshold for the respective hypothesis is set to 90% SADE-free rate, which allows for comparison with preceding studies, such as the DF4 Master Study, the Iperia/Sentus QP Master Study and the BIO|MASTER.Ilivia Family/Plexa study, which have used the same value, and which is known to be accepted by authorities outside of Europe who might also be provided with results from this study in the course of regulatory approval submissions. The safety endpoint will be evaluated using the data collected at implantation until the 3-month follow-up-, as the majority of, for example pocket infections, is found within this early postoperative phase^{3,35}.

Three secondary endpoints were defined:

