7.2 Endpoints and hypotheses

7.2.1 Primary endpoint and hypotheses: Cor Family-related SADE-free rate until 3-month follow-up

The safety of the Cor Family ICDs will be evaluated by asking the investigator to record any adverse event. While all adverse events have to be recorded throughout the study, only the Serious Adverse Device Effects (SADE) possibly or securely related to the Cor Family devices (SADE-d_{Cor}) until 3-month follow-up are counted for this primary endpoint. Purely procedure related Serious Adverse Device Effects (SADE-p_{Cor}) are not counted. Further definitions are given in section 18.5.1. The primary hypothesis evaluates the SADE-d_{Cor} free rate (Cor_{SADE_free}). It is expected, that the rate will be significantly above 90%, the corresponding hypotheses definitions are:

Null hypothesis: $H_0_{Cor} : Cor_{SADE_free} \leq 90\%$

Alternative hypothesis: $H_{A_{Cor}} : Cor_{SADE_free} > 90\%$

The parameter of interest "Cor_{SADE_free}" is the rate of device-related SADE-d free patients, which will be calculated by

$Cor_{SADE_free} = [1 - \text{number of patients with one or more ICD related SADEs (SADE-d}_{Cor}\text{)} \text{ until 3-month follow-up divided by all patients in the analysis set}] * 100\%.$

The following patients are not included in the analysis set for this endpoint:

- Patients without endpoint but premature study termination before or exactly at 61 days after implantation (3 months defined as 92 days after implantation – 30 days would still be in accordance to the CIP) are not included in the analysis set to avoid an over-estimation of the SADE-free rate.

SADEs will be adjudicated by an internal adjudication board, whereby the seriousness and device relatedness will be re-examined. If any amply documented external physical influence (e.g. accident, sport, twiddling) or medical AE caused the SADE, it does not contribute to this endpoint. SADEs that occur later than the 3-month follow-up, and SADEs with onset date later than or exactly at 123 days after implantation (3 months defined as 92 days after implantation + 30 days would still be in accordance to the CIP) in case the 3-month follow-up was not conducted or conducted outside the specified time interval do not contribute to this endpoint.

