20 SUSPENSION

20.1 Criteria and procedures

Suspension or premature study termination may occur due to several reasons:

- On behalf of the sponsor
- On behalf of the investigator
- On behalf of the EC

The sponsor is authorized to terminate the clinical study prematurely due to relevant medical/organizational reasons.

A consultation of all parties involved prior to study termination is preferable. Reasons for premature study termination should be documented in an adequate way.

The sponsor has the right for premature study termination of the whole study, of single study phases or arms, or to exclude single investigational sites from further study participation.

Reasons for termination may be:

- Occurrence of severe Adverse Events that result in a non-acceptable risk for further study participation.
- The number of premature study terminations exceeds the tolerable percentage of drop-outs so that proper completion of the study cannot be expected anymore.
- In case that the number of drop-outs is lower than expected, enrollment can be stopped earlier as soon as 114 patients are included in the analysis set of the primary endpoint. Patients are included in the analysis set if they completed at least 61 days after implantation in the study or if they experienced a primary endpoint before that date.
- Insufficient enrollment rates so that proper completion of the study cannot be expected anymore.
- Results from other clinical investigation indicate a non-tolerable risk for further conduction of this study.
- Attempted fraud or fraud that may be evidenced.
- Poor data quality.
- Missing compliance of the respective investigator or study site (e.g. protocol violations).

In case the study sponsor decides to suspend or prematurely terminate the study, the sponsor is required to promptly notify the investigator(s) to whom the decision applies. The investigator will inform the EC of this decision. The investigator will also promptly inform all patients enrolled at the investigational site and are still actively participating. Patients that already left the study shall be informed if they might be affected by safety aspects.

In case of any reasonable ethical concern of the investigator regarding a further study conduct in the respective investigational site, the sponsor shall be informed immediately.

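### Eligibility violators are dropped from the primary safety set and from its Kaplan-Meier sensitivity analysis even if they were implanted and had a device-related SADE

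*Protocol*

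**What the plan says.** CIP 11.12 lists three grounds for leaving a patient out of the primary analysis set: no documented consent, an eligibility violation, and early termination without an endpoint. The second reads "Patients that are erroneously enrolled despite violation of inclusion or exclusion criteria at the time of enrollment". Only the third is restricted to patients who have had no endpoint. SAP 5.5 copies the list, and SAP 11.1 applies it to the Cor Family analysis set.

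CIP 7.2.1, where the endpoint is defined, names a single exclusion: "Patients without endpoint but premature study termination before or exactly at 61 days after implantation". Its stated purpose is to keep the SADE-free rate from being overestimated.

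For the Kaplan-Meier estimate, which serves as the sensitivity analysis for the primary endpoint, CIP 7.2.2.1 says that every patient is to be analysed. SAP 12.1 instead removes the eligibility violators, as in the primary analysis.

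CIP 20.1 allows enrollment to stop once 114 patients are in the primary analysis set, and describes membership this way: "Patients are included in the analysis set if they completed at least 61 days after implantation in the study", or if they had an endpoint before then. It has no eligibility condition.

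**The concern.** The primary objective is to confirm the safety of the devices. A device failure in an implanted patient is evidence about the device whether or not an enrollment criterion was breached, so a safety rate should count everyone exposed. The plan recognises the direction of bias in its early-termination rule, which keeps patients with events in the set. The eligibility rule has no such protection: a violator with a device-related SADE leaves both numerator and denominator.

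The study is open and single-arm, and events are adjudicated by an internal board. A breach present at enrollment may be noticed only later, for instance when an SADE prompts a closer look at the chart. Because SAP 12.1 drops the same patients, the planned sensitivity analysis would not bring the event back. At stake is the single confirmatory test, where the result can turn on one patient.

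**Working it through.** **Inputs.** Null: "The threshold for the respective hypothesis is set to 90% SADE-free rate" (CIP 5.3). Alternative: "a SADE-free rate in the population of 98% was assumed" (CIP 11.2). Test: exact binomial (CIP 11.2). Level: "a two-sided p value less than 5% will be considered statistically significant" (CIP 11.3), taken as 2.5% in the relevant tail. Power: at least 95%, at the given and any larger sample size (CIP 11.3). Drop-out: about 10% (CIP 11.4).

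**Reproducing the plan.** Let X be the number of patients with a primary-endpoint SADE among n. The test passes if P(X ≤ x | n, 0.10) ≤ 0.025; let c(n) be the largest such x. Power is P(X ≤ c(n) | n, 0.02). The smallest n with power of at least 95% there and at every larger n checked is 114. There c = 5, the attained one-sided level is 0.0239 and power is 97.3%. Then 114/0.90 = 126.7, rounded up to 127. Both planned figures reproduce.

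**Removing one violator who had an event** turns x of n into x − 1 of n − 1.

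| Before | one-sided p | After | one-sided p | Change |
|---|---|---|---|---|
| 6/114 | 0.0544, fail | 5/113 | 0.0255, fail | none |
| 6/115 | 0.0513, fail | 5/114 | 0.0239, pass | fail to pass |
| 7/127 | 0.0538, fail | 6/126 | 0.0266, fail | none |

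For 6/115 the lower limit of the exact 95% interval for the SADE-free rate is 88.99%; for 5/114 it is 90.06%.

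c(n) is 5 for every n from 114 to 126, so 6 events fail at any starting n from 115 to 126, and 5 events at n − 1 pass. If one SADE patient could always be removed, the one-sided type I error would be 0.0513 at n = 115, falling to 0.0266 at n = 126.

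The result at 127 is close and depends on the tail convention: 6/127 passes with a tail probability of 0.02499. Under the minimum-likelihood two-sided p-value it is 0.0526 and fails, so the flip would also be possible there.

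**Removing an event-free violator** goes the other way. With 5 events, 110/115 = 95.65% becomes 109/114 = 95.61%.

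**How often this would matter.** The documents give no violator count. Assume 1% to 5% of patients, unrelated to outcome.

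- Chance that at least one of 127 patients is a violator with a SADE, 1 − (1 − q × r)^127 for violator share q and SADE rate r: 2.5% to 12% at r = 2%, and 12% to 47% at r = 10%.
- Chance of the illustrated flip at n = 115: P(X = 6) is 2.0% at a 2% rate and 2.9% at a 10% rate. At least one of the six is a violator with probability 1 − 0.99^6 = 5.9% to 1 − 0.95^6 = 26.5%. The products are about 0.1% to 0.5%, and 0.2% to 0.8%.

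**Early enrollment stop.** If enrollment stops at 114 counted under CIP 20.1 and one event-free patient is then dropped under CIP 11.12, n = 113. Then c = 4 and power is 92.3%, below the planned 95%.

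**The case against.** The best defence is that the exclusion is written down in advance and tied to status at enrollment. Criteria are checked before enrollment and recorded on the eCRF (CIP 9.2), deviation forms are triggered from data entry (CIP 14.2), an early monitoring visit is planned (CIP 10), and the biostatistician does a review that the plan calls blind before the final analysis (CIP 12.3). These steps make late recognition less likely but do not rule it out. None of them says that eligibility violations are settled before adjudication or without knowledge of events. The text of the SAP footnote attached to this exclusion is not visible and may say more.

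A reader might infer that the plan allows events to be struck out by a rule invented afterwards. The documents do not support that; the open matter is only when, and with what knowledge, a violation is recognised. A reader might also infer that CIP 7.2.1, 11.12 and 20.1 leave the confirmatory test with three competing denominators. They do not. SAP 11.1 combines 11.12 with 7.2.1 into one operative set, and 20.1 governs only when enrollment may stop. The removal of an event follows from 11.12 and SAP 11.1 alone.

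It is also fair that most removed violators would be event-free if the planned rate holds, which slightly disadvantages the device, and that the 115-to-114 example is a boundary case. The SADE would not vanish from safety reporting either, since adverse events go into the Vigilance AE report (SAP 8.2.11). All of this stands and limits the size of the point. It does not explain why an exposed patient's event should leave the safety test, or why SAP 12.1 departs from CIP 7.2.2.1.

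**Conclusion.** The point holds in a limited form. A device-related SADE in an implanted eligibility violator is removed from the primary test and from its sensitivity analysis, and SAP 12.1 contradicts CIP 7.2.2.1. One such removal can change fail to pass for starting sizes 115 to 126, but not at 114 or 127 under the 2.5% tail rule. Under the assumed 1% to 5% violators unrelated to outcome, the illustrated flip has a chance below 1%. It would be likelier if recognition of violations were linked to events, which the documents neither show nor exclude.

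The day-61 difference (CIP 7.2.1 excludes an event-free termination on exactly that day, CIP 20.1 counts it) is editorial. The sample size calculation is sound and is not affected.

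**What to change.** Delete the eligibility-violation exclusion in CIP 11.12 and in SAP 5.5, 11.1 and 12.1; changing only some of these would create a new inconsistency.

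- **Primary set:** all consented patients with a Cor Family implantation attempt, minus event-free terminations on or before day 61.
- **Kaplan-Meier set:** all consented patients with a Cor Family implantation attempt.
- **Sensitivity analysis:** the primary analysis without violators, with the list of violations settled before adjudication.
- **Editorial:** in CIP 20.1, count patients towards 114 by the same set, with more than 61 days completed.

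The cost is a wording change to both documents; CIP 11.8 allows the SAP to be updated until database freeze. The 114/127 sample size, the limit of 5 SADE patients at n = 114 and the 97.3% power are unchanged. The one downside is that the estimate may become slightly less favourable.
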